In addition, attractive and informative packaging plays a crucial role in building a brand name (Keller KL, 2005). Studies have shown that recognized and reputable brand names are associated with increased consumer acceptance and adherence compared to generic drugs (Rafael GB et al, 2019; Faasse K, et al, 2013; Faasse K, et al, 2016). Thus, understanding women's and their partners' preferences regarding packaging design can help create a brand for antenatal MMS that is delivered through the national health system that promotes optimal use throughout pregnancy.

2. Study aims and objectives

This study aims to assess the relevance, acceptability, and utility of three interventions in supporting adherence to the MMS regimen of one tablet per day. The overall aims of the study are to:

1. Learn what pregnant women prefer regarding visual reminders and motivational messages to help them remember to take their MMS.
2. Identify challenges and supports that affect whether women can take their MMS daily throughout their pregnancy.
3. Work with end users (pregnant women) to design motivational messages and visual reminders that are culturally appropriate and relevant for the local community. These will be designed to help women consistently take one MMS tablet each day for the entire 180 days of their pregnancy.
4. To collect feedback from pregnant women and their partners regarding the packaging design for antenatal MMS delivered through the national health system. This feedback will be used to help finalize the MMS packaging design, including the color scheme, logo, brand name, and packaging features.

3. Study design

This is a longitudinal mixed-method study that uses a cross-over TIPS design. All enrolled pregnant women will be asked to take MMS for the duration of their pregnancy and will experience all three interventions in a specific order. In this way, everyone gets to experience each approach. The women will receive exposure to each intervention for 3-4 weeks. On approximately the fourth week, eighth week, and twelfth week of the study, the pregnant women will be asked to participate in a focus group discussion (FGD) with other women in the province who also received the same intervention the previous weeks. This process will be iterated in the same way for Intervention A, Intervention B, and Intervention C.

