For the TIPS, the sample size of 48-60 women (around 12-15 women per province) is purposive but has been selected for two reasons. First, the sample size of 12-15 women per province allows enough women to participate in a FGD. Considering that an ideal number for FGD is 8-10 people if 20% of the participants are expected not to show, there would still be enough participants to conduct an FGD. Second, based on previous formative research with pregnant women in Kampong Thom, there was not much variation in the experiences of women regarding MMS acceptability and their perceptions of the benefits of various strategies to improve adherence. Thus, one FGD per province is believed to be sufficient to capture the range of perspectives on the different interventions and achieve saturation, or the point at which no new significant themes or insights emerge from the data.

For the participatory workshops to design the MMS product package, approximately 100 participants will be recruited across four provinces in Cambodia (25 participants per workshop, 4 workshops total). Participants will be pregnant women who have previously participated in the TIPS program and their husbands/partners. The sample size is a convenience sample and chosen for the following reasons. First, it is anticipated that with a focused group like pregnant women and their partners who have a shared experience with the TIPS program, 25 per province is likely enough to reach saturation. Second, the study must consider logistical manageability and group dynamics. With 25 participants, workshops can maintain a manageable size for group discussions and activities. This allows for active participation, ensures everyone has a chance to be heard, and facilitates effective interaction. Thirdly, smaller workshops require fewer facilitators, materials, and space, making them more cost-effective and easier to organize across four different provinces.

6. Participant recruitment and selection

The research team will aim to recruit 12-15 pregnant women attending their first ANC per province. Ideally, from 8-10 of these women will then join the FGD to discuss their experiences with that specific intervention (see Table 1).

Figure 1. TIPS sample size per province

Week	Interventions	Kampong Chhnang	Rattanakiri	Takeo	Kampot	Total
1-3	A	12-15	12-15	12-15	12-15	48-60
4	Focus Group Discussions					
5-7	B	Same women	Same women	Same women	Same women	
8	Focus Group Discussions					

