Selected healthcare providers (e.g. midwives, doctors) from the primary health center will attend an orientation and training on the objectives and design of the study, the benefits of IFA or MMS supplementation during pregnancy, and any expected risks with participation. Healthcare providers will be trained on the protocol for enrollment (e.g., inclusion and exclusion criteria), obtaining verbal consent, and recording registration data. A primary healthcare worker in the health center (receiving an incentive payment from the study) will invite pregnant women to participate, give an overview of the study, including any risks, and ensure they meet all inclusion criteria. Healthcare workers will obtain verbal informed consent, provide the MMS-180, and explain that the study team will contact the participants within 72 hours and visit them in their homes to obtain written informed consent. If the woman agrees, she will provide her contact number, which the healthcare worker will submit to the study team by the end of the day. The women will then receive MMS-180 and be counseled on its use. A member of the study team will reach out to the new participant ideally within 72 hours to confirm participation, informed consent, and that the woman received the supplements. Up to two weeks will be allowed from the time of verbal informed consent at the health center until written consent is obtained at the participant's home. A record of all women screened but not enrolled will be maintained. The enrollment form is included in Annex A and the informed consent form for TIPS is included in Annex B. The informed consent form for the participatory workshop is in Annex C.

7. Study procedures

In each of the four health centers, a designated healthcare provider will enroll up to 15 pregnant women with first ANC visit. All women will receive all three interventions (family support, wall calendars, social media posts and videos) sequentially over 12 weeks. Women will be exposed to each intervention for 3-4 weeks, followed by a FGD to share their experiences and feedback. This iterative process helps researchers improve the interventions for better MMS adherence during pregnancy.

7a. Participant allocation

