At each FGD, pregnant women will be asked to bring with them their MMS bottle. At the end of each FGD, the research team will conduct a tablet count. The research team will explain that they will quickly count the woman’s remaining MMS tablets by transferring the pills to a clean bag, counting them, and then returning them without touching them. After putting on fresh gloves, the trained researcher will open the medication bottle, pour the pills into a sealed bag, and place all pills flat with pills on one side. Using gloved hands, the researcher will count the pills, moving them one by one or grouping them by ten for easier counting. The count will be recorded twice. If the counts differ, they will repeat the process once more and record the final number. Finally, a small corner of the bag will be snipped, and the pills with the desiccant will be carefully poured back into the bottle before securing the lid. See Annex G for the tablet count sheet.

7g. Acceptability survey

During the FGD with pregnant women, all participants will be asked to fill out a survey to gather their opinions on various sensory aspects of the MMS. The survey will inquire about their preferences regarding the taste, smell, size, color, and ease of swallowing the pill. Participants will be asked to rate their opinions on a scale ranging from "strongly disagree" to "strongly agree," with options including "disagree," "neutral," and "agree." Each option will be represented by a corresponding mood emoji on the survey form. The survey is designed to be completed within 5 minutes and will be administered at the conclusion of the FGD. See Annex H for a copy of the acceptability survey form.

7h. Incentives for participants

Mobile data (KHR 15,000) will be provided for all women to see the social media posts and videos. In addition, a sarong, a towel, local fruits, or local nutritious food products (e.g. fish powder, dried fish) will be provided after each FGD and/or participatory workshop to respect participants’ time and valuable participation in the FGDs and/or participatory workshop. These items were selected as incentives as they are believed to be valuable enough to show appreciation to respondents for their time, but not so valuable that they will cause undue influence in study participation.

8. Data collection methods and tools

Tool	Purpose	Annex No.

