From pill count data, descriptive analysis will be performed to measure daily adherence to MMS. During each focus group discussion, we will count the MMS tablets for each participant and calculate the eligible period for consumption from the 1st ANC date (pill received date) to the date of the focus group discussion. The mean number of tablets consumed will be calculated based on the eligibility of the consumption period. Adherence will be measured after the completion of each intervention, and differences in the mean will be measured. However, due to a very low sample size, no statistical test will be applied.

10c. Acceptability data

At the first focus group discussion, data collectors will ask pregnant women a quantitative acceptability questionnaire about MMS. A descriptive analysis will be conducted to determine the level of agreement (%) with each statement. However, due to a very low sample size, no statistical test will be applied.

11. Data custody, security, and protection of subject confidentiality

All data gathered during the study will be connected to identifiers and treated with the utmost confidentiality throughout and beyond the study period. Only the study's PIs and Co-PIs will have access to the data linked to the identifiers. The results of any analyses, presentations, or papers will be presented in aggregate to prevent individual disclosure. The survey will collect names of pregnant women only to ensure the accountability of the study team and to avoid duplication in the data collection/interviewing process. This information will be replaced with anonymous ID numbers for analysis, and the original data will be disposed of. Only members of the study team will be given access to the data.

Any paper notes collected during interviews will be kept in a locker until the final analysis is done. Once the analysis is done, all paper forms will be cut into pieces using a paper shredder machine. The data entry web-based platform will be password protected, and only a designated person can enter data. The data focal person will only have access to download and clean.

12. Risks and Benefits

Overall, the potential benefits of this study outweigh the minimal risks.

Benefits:

- Improved micronutrient status and improved birth outcomes: MMS is a proven effective intervention that improves maternal micronutrient status as well as improves birth outcomes, specifically reduces low birth weight, small for gestational weight, and pre-term births.

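### The plan does not say when interventions B and C start relative to the preceding tablet count, so up to 6 of the 28 days between counts can belong to the previous intervention

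*Combined protocol and SAP*

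**What the plan says.** Figure 1 (section 6) and Figure 2 (section 7c) use the same week grid: A in weeks 1-3, B in weeks 5-7, C in weeks 9-11. Weeks 4, 8 and 12 name no intervention as running; in Figure 1 they read only "Focus Group Discussions".

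The text is looser. Section 3 states: "The women will receive exposure to each intervention for 3-4 weeks". It places the focus group discussions (FGDs) "On approximately the fourth week, eighth week, and twelfth week of the study". Section 7 repeats the range and the order: "Women will be exposed to each intervention for 3-4 weeks, followed by a FGD to share their experiences and feedback". It gives the total as well: "All women will receive all three interventions (family support, wall calendars, social media posts and videos) sequentially over 12 weeks".

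On measurement, section 7f says: "At the end of each FGD, the research team will conduct a tablet count". Section 10b will "calculate the eligible period for consumption from the 1st ANC date (pill received date) to the date of the focus group discussion", and continues: "Adherence will be measured after the completion of each intervention, and differences in the mean will be measured". It plans no statistical test.

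**The concern.** To attribute adherence to an intervention, the days over which tablets are counted should be the days on which that intervention was in use. The figures end each counting interval in an FGD week but start the next intervention only in the following week. Any days between the FGD and that start fall into the new intervention's interval while the woman is still on the previous one. The comparison of B with A, and of C with B, is then partly a comparison of an intervention with itself.

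This matters because section 3 says the crossover lets the researchers see which approach works best, and the tablet count is the only objective measure of that. Having no significance test does not help: misplaced days shift a descriptive mean in the same way. The plan also does not ask for each woman's start date on B or C, so the mismatch could not be corrected afterwards.

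**Working it through.** **Inputs.** Number the days from the start of week 1. Week 4 is days 22-28, week 8 is days 50-56, and B as drawn is days 29-49 (21 days). Let the counts fall on day a in week 4 and day b in week 8. The interval holds the days after the first count up to and including the day of the second, so its length is b - a.

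**1. The plan's own total.** 3 x (3 weeks + 1 FGD week) = 12 weeks. 3 x 4 weeks with the FGD inside the fourth week is also 12. 3 x (4 weeks + a separate FGD week) = 15, which does not fit. The stated 12 weeks therefore fits both the figures and contiguous four-week blocks, and cannot decide between them.

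**2. Days outside B's scheduled weeks.** Share = (b - a - 21) / (b - a).
- Counts 28 days apart: 7/28 = 25.0%.
- Shortest spacing (a = 28, b = 50): 1/22 = 4.5%.
- Longest spacing (a = 22, b = 56): 13/34 = 38.2%.
- Exposure from FGD to FGD: 0/28 = 0%.

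**3. Which of those days come before B starts.** Before B: 28 - a, which is 6 days (a = 22) down to 0 (a = 28). After B's scheduled weeks: b - 49, which is 1 day (b = 50) up to 7 (b = 56). At 28-day spacing the two always add to 7. The largest share before B is 6/28 = 21.4%. This holds for any pair of days, because the shortest interval starting on day 22 is 28 days. Assigning the day of the first count to the later interval instead would shift the range by one day, to 1 to 7. C gives the same result: counts in weeks 8 and 12, start on day 57, and 56 - a = 6 to 0 days before C.

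**4. Effect on the comparison.** Let the new intervention change adherence by d points (an assumption; the plan gives no effect size). Suppose that the p days before its start behave like the previous condition and the days after its scheduled weeks behave like the intervention itself. With counts 28 days apart, observed change = d x (28 - p)/28.

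| Assumed d | p = 0 | p = 6 |
|---|---|---|
| 5 | 5 | 5 x 22/28 = 3.9 |
| 10 | 10 | 10 x 22/28 = 7.9 |
| 20 | 20 | 20 x 22/28 = 15.7 |

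**5. The denominator in section 10b.** As written, each interval starts at pill receipt. Taking day 1 as pill receipt and start of A, and counts at days 28, 56 and 84, the share of counted days outside the named intervention is 1 - L/T, where L is the block length and T the count day.

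| Count | 3-week blocks (L = 21) | 4-week blocks (L = 28) |
|---|---|---|
| A, T = 28 | 25.0% | 0% |
| B, T = 56 | 62.5% | 50.0% |
| C, T = 84 | 75.0% | 66.7% |

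Correcting the schedule alone would therefore leave half (B) to two thirds (C) of the counted days belonging to earlier interventions. Subtracting successive counts alone would leave the 0 to 6 days in step 3.

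**The case against.** The strongest reply is that no gap is established. Figure 1 is a coarse grid, titled as a sample size table. The text permits three contiguous four-week blocks, each closed by an FGD, and nothing says that an intervention stops before its discussion. Section 7c has family reminders continuing until the 180 tablets are used up, and no section says that calendars are taken back. In addition, section 10b does not use the days between counts as its denominator, and the results are descriptive.

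Much of this stands. A reader might infer from the figures that women spend a full week on no intervention, that a quarter of the days is the upper limit, or that a 10-point effect would shrink to 7.5. The documents do not support any of these. The quarter is the value at 28-day spacing, not a maximum. The days after B's scheduled weeks may well be days on B. And the cumulative denominator in section 10b mixes in more earlier-intervention time than the FGD week does.

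The reply does not dispose of the start date. A range of 3-4 weeks can stretch an intervention forward to its own FGD. It does not move the next start back to the preceding count, and both figures put that start in the following week. No section says otherwise.

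A further objection is practical: section 5 expects 20% of women not to attend, and they would miss a calendar handed out at the FGD. This adds little, because under the current plan too every woman must receive the calendar.

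**Conclusion.** The point holds as a schedule ambiguity with a modest, bounded effect. The figures leave weeks 4, 8 and 12 unassigned and start B and C a week later, and the text does not fix the start relative to the count. On the figures as drawn, 0 to 6 of 28 days (0-21%) can carry the previous condition into the next interval, so an assumed 10-point effect would appear as about 7.9 to 10 points. If the next intervention in practice starts at the FGD, the effect is nil.

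The size rests on three assumptions: counts 28 days apart, adherence calculated from count to count, and days before the start behaving like the previous condition. Under section 10b as written, the larger distortion is the cumulative interval. The consequence is confined to the descriptive adherence means; the qualitative findings on preference and acceptability do not depend on it.

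**What to change.** - Reconcile Figures 1 and 2 with the text. Start each next intervention at the FGD, straight after the tablet count: the calendar at the end of the discussion of A, the first links at the end of the discussion of B. Redraw the blocks as weeks 1-4, 5-8 and 9-12, each closed by the FGD and count. This fits the stated 12 weeks and the upper end of the 3-4 week range.
- Deliver the calendar to women who miss the FGD by the route already needed to reach them.
- Record each woman's actual start date for each intervention beside her count dates.
- In section 10b, calculate adherence from one count to the next. Without this, the schedule change cannot have its full effect.

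The cost is mainly wording, plus one date per woman and intervention. The downside is that the calendars and posts must be ready up to a week earlier than the figures imply. The tablet regimen is not touched.

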- Approximately 3 social media videos and posts will be developed.
- The videos and posts might cover topics like:
 - The importance of MMS for maternal health and growing baby's health.
 - Benefits of consistent medication adherence.
 - Benefits of healthy eating.
 - General pregnancy care information and warning signs.
 - Reminders to attend prenatal checkups.

After using each intervention for 3-4 weeks, women will be invited to a FGD to share their experiences. The discussion will focus on whether they liked the intervention, how well it helped them remember to take their MMS and any pros and cons they saw. It will also ask the women to compare the current intervention with other intervention (i.e. family support, wall calendars, and public service announcements). Adherence data will be collected by asking women to bring their MMS pill bottle to the FGD for counting. Acceptability data will be collected through a Likert survey and will be administered by a member of the study team.

By using this TIPS crossover design, researchers can see which approach works best and use the women's feedback to improve the program throughout the study. This collaborative process, where participants try different interventions and share their experiences, allows researchers to refine the program iteratively (meaning in steps) based on the feedback, resulting in a more effective program by the end of the study.

4. Study setting

The research will be conducted in Kampong Chhnang, Rattanakiri, Takeo, and Kampot, representing the four regions in Cambodia: Coastal, Upland (Northeast), Lowland, and Tonle Sap.

5. Sample size calculation and sampling process

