9-11	C	Same women	Same women	Same women	Same women	
12	Focus Group Discussions					
Total		12-15	12-15	12-15	12-15	48-60

The study participants will include approximately 48-60 pregnant women attending their first ANC in their first trimester at a public health center. Approximately 48-60 pregnant women will be recruited across 4 health centers in Kampong Chhnang, Rattanakiri, Takeo, and Kampot. It is estimated that approximately 12-15 pregnant women will be enrolled per province. Pregnant women will be purposively recruited at their **first antenatal care visit** (~8-14 weeks gestation). An attempt will be made to select women of diverse sociodemographic characteristics.

For the participatory workshops to co-design the MMS package, we plan to invite all women and their husbands enrolled in the TIPS study design. The first 25 from each province who agree to participate will be registered to attend the participatory workshop. We will aim to have a relatively equal proportion of men and women.

6a. Inclusion criteria for pregnant women

- Age 18-45 years
- Attending first ANC
- Low-risk pregnancy, which includes being pregnant with a single pregnancy and the absence of any other medical or surgical conditions
- Reside in Kampong Chhnang, Rattanakiri, Takeo, and Kampot and not planning to move away within four months
- Agree to try to take MMS as their prenatal supplement
- Agree to participate in three FGDs, one every three months
- Agree to bring MMS bottles to the FGD each month for tablet counting

6b. Exclusion criteria for pregnant women

- Pregnant women who do not fall into the age range of 18-45
- Came to the health facility after first ANC
- Midwives and/or doctors have classified pregnant women as having a high-risk pregnancy.

6c. Inclusion criteria for husbands

- Willingness to participate in the participatory workshop
- Confirmed availability for date and time of workshop

6d. Exclusion criteria for husbands

- Unwillingness to participate in the participatory workshop
- Did not confirm availability for the date and time of workshop

6e. Recruitment process and taking informed consent

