There is no allocation to any intervention group. Each enrolled woman receives all interventions in a specific sequence. Per province, in each health facility, the study team will purposively select pregnant women to ensure a diversity in sociodemographic characteristics. This helps ensure the interventions are appropriate for a broad range of women. After ensuring written informed consent, the eligible pregnant women will be asked to participate in taking MMS and arm experience all three interventions (A, B, and C) in a specific order. The sequence for each study arm and their exposure to the intervention is shown in Figure 2. This allows researchers to compare a participant's experience with each intervention.

7b. Enrollment data

Demographic and other enrollment data, such as gestational age at enrollment, maternal age, maternal BMI, maternal Hb, parity, as well as contact information and detailed directions to home of residence, will be collected from the health facility. This data will be included in the analysis for adherence, acceptability, and barriers and enablers.

7c. Intervention description

- **Intervention A (MMS + Family support):** 180 tablets of MMS and daily encouragement and help from family members. Family members will receive an orientation on supporting pregnant women and encouraged them to provide daily motivational reminders until she finished 180 pills
- **Intervention B (MMS + Visual reminders):** 180 tablets of MMS and wall calendars with health information and motivational messages will be provided.
- **Intervention C (MMS + Social media posts and videos):** 180 tablets of MMS and 2-3 times/weekly social media posts and videos educational and motivational messages from healthcare providers delivered through social media posts and videos. Messages will emphasize its benefits and offer encouragement.

Figure 2: Weeks 1-14, Testing of interventions across all study arms and participant FGDs

Intervention	Week 1-3	Week 4	Week 5-7	Week 8	Week 9-11	Week 12	Week 13-14
A	Intervention A	Focus Group Discussion A	Intervention B	Focus Group Discussion B	Intervention C	Focus Group Discussion C	Participatory Workshop
B	X	X					X
C			X	X	X	X	X

7d. Conduct of focus group discussions

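### Section 6a asks women to agree to focus groups three months apart, but the plan holds them about four weeks apart

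*Combined protocol and SAP*

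**What the plan says.** The eligibility list in section 6a contains three statements that bear on FGD timing:

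- the FGD commitment: "Agree to participate in three FGDs, one every three months";
- the next bullet, on pill counts: "Agree to bring MMS bottles to the FGD each month for tablet counting";
- the residence requirement: "not planning to move away within four months".

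The schedule itself is set elsewhere:

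- Section 3: "On approximately the fourth week, eighth week, and twelfth week of the study, the pregnant women will be asked to participate in" an FGD. Later in that section: "After using each intervention for 3-4 weeks, women will be invited to a FGD to share their experiences".
- Section 7: the three interventions are delivered "sequentially over 12 weeks".
- Figure 1 (section 6) and Figure 2 (section 7c, captioned "Figure 2: Weeks 1-14, Testing of interventions across all study arms and participant FGDs") put the FGDs in weeks 4, 8 and 12.
- Section 3 places the closing packaging workshop in week 13 or 14.

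Under section 6e, the recruiting health worker invites women and must "ensure they meet all inclusion criteria"; providers are trained on the inclusion and exclusion criteria beforehand.

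**The concern.** The number of FGDs, three, is the same throughout. The spacing is not. One criterion implies quarterly meetings and the next implies monthly ones, so the list contradicts itself as well as the design.

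This is operative text. It describes the commitment a woman is asked to make, and staff apply it at the point of enrolment. Read literally, it understates how often she must attend by a factor of about three. She could enrol with the wrong expectation, or be declined because she cannot commit to meetings spread over many months. Tablet counts are taken at the FGDs (section 7f), so missed meetings would also mean missed adherence measurements.

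**Working it through.** No sample-size or power formula applies; this is calendar arithmetic.

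**Inputs**

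- FGD interval in the criterion: 3 months (section 6a).
- Planned FGDs: weeks 4, 8 and 12 (section 3, Figures 1 and 2).
- Study end: week 13 or 14 (section 3, Figure 2).
- Residence window: 4 months (section 6a).
- Gestation at enrolment: about 8 to 14 weeks (section 6).
- Conversion: 365.25 / 12 / 7 = 4.348 weeks per month, so 3 months = 13.0 weeks and 4 months = 17.4 weeks.
- Assumption: study week 1 begins at enrolment.

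**Step 1: reproduce the planned schedule.** Three cycles, each with 3 weeks of intervention and 1 FGD week: 3 × (3 + 1) = 12 weeks. FGDs fall at weeks 4, 8 and 12, which agrees with section 3, section 7 and both figures. The interval is 4 / 4.348 = 0.92 month, which agrees with the monthly bottle criterion. The third FGD is at 12 / 4.348 = 2.76 months, inside the four-month window.

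**Step 2: compare the spacing.** Ratio of stated to planned interval: 13.0 / 4 = 3.25. Span from first to third FGD: 2 × 13.0 = 26.1 weeks (unrounded months), against 12 − 4 = 8 weeks planned.

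**Step 3: test the fit without choosing a start date.** The span alone, 26.1 weeks, exceeds both the 14-week study and the 17.4-week residence window. No choice of first FGD date can make the three-month interval fit either.

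**Step 4: place the FGDs under each possible start.**

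| Reading | FGD weeks | FGDs by week 14 | Third FGD relative to the 17.4-week window |
|---|---|---|---|
| Planned | 4, 8, 12 | 3 of 3 | 17.4 − 12 = 5.4 weeks inside |
| Three-monthly, first at week 4 | 4, 17, 30 | 1 of 3 | 30.1 − 17.4 = 12.7 weeks after |
| Three-monthly, first at month 3 | 13, 26, 39 | 1 of 3 | 39.1 − 17.4 = 21.7 weeks after |
| Three-monthly, first at enrolment | 0, 13, 26 | 2 of 3 | 26.1 − 17.4 = 8.7 weeks after |

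The last row is included for completeness. It is not workable, because each FGD is meant to follow a period of using an intervention.

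**Step 5: gestation at the third FGD.** Planned: 8 + 12 = 20 to 14 + 12 = 26 weeks. First at week 4: 8 + 30 = 38 to 14 + 30 = 44 weeks. First at month 3: 8 + 39 = 47 to 14 + 39 = 53 weeks, which is beyond any pregnancy.

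**Sensitivity.** Section 6e allows up to two weeks between verbal and written consent, and section 7a starts the interventions after written consent. With the full delay the upper ends in step 5 become 28, 46 and 55 weeks. The planned third FGD would then be 12 + 2 = 14 weeks after screening and the workshop at most 14 + 2 = 16 weeks after, both still inside 17.4. The conclusion does not change.

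**The case against.** The strongest reply is that this is a slip of the pen, perhaps for one meeting a month over three months, and that the rest of the protocol corrects it. Every other statement of timing agrees, and the very next bullet is monthly. The criterion also does not set the timing: under section 7d the research team invites women once they have completed an intervention period and schedules each FGD. Section 10b computes adherence from the date tablets were received to the actual FGD date, so the calculation itself does not use the phrase. Staff are trained on the design as well as the criteria, and a home visit for written consent gives a second chance to explain the schedule. That a woman would be wrongly declined is speculative. The four-month residence criterion suits the real schedule and conflicts only with the faulty phrase, so it corroborates the slip and is not a separate defect. The gestation projections likewise show that the phrase cannot be meant; they do not measure harm.

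Most of this stands, and it limits the weight of the point. A mistaken expectation of meeting frequency is the more plausible consequence; wrongful exclusion is less so. The link to pill counts runs only through attendance. But a likely intention does not make the written criterion consistent, and staff are told to check the criteria as written. The enrollment and consent forms are not in the reviewed text, so whether they carry the right schedule is unknown.

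**Conclusion.** The criterion is wrong as written, and the severity is minor. It states an interval of about 13 weeks where the plan uses 4, and a first-to-third span of about 26 weeks where the plan uses 8. Nothing in the documents supports a three-month interval.

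That the span cannot fit the study or the residence window rests only on converting months to weeks. The individual FGD dates and gestational ages also depend on when the first FGD is held and on study week 1 starting at enrolment. The effect on enrolment or attendance cannot be estimated from the documents. Sample size is unaffected, and the pill-count analysis is descriptive with no test.

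**What to change.** Reword the section 6a bullet to match section 3 and Figures 1 and 2, for example: agree to participate in three FGDs, one about every four weeks (approximately weeks 4, 8 and 12). The bottle and residence criteria can stay as they are.

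Then confirm that the screening script, staff training material, enrollment form and consent form give the same schedule. The cost is one line in the eligibility list and a wording check of those materials; design and analysis are untouched.
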